7.7.1.2. Primary Analysis

There is one planned futility analysis of PFS and final analysis of PFS.

- The futility analysis will utilize PFS by investigator assessment, and take place after approximately [REDACTED] progression events have been observed. Futility will be declared if the observed hazard ratio is [REDACTED]. See Section 7.12.2.
- The primary analysis of PFS will utilize PFS by BIRC to test the superiority of the abemaciclib arm to the control arm using use a Bayesian decision rule. The abemaciclib arm will be considered superior if the posterior probability that the hazard ratio for PFS is [REDACTED] is [REDACTED] than [REDACTED]. Details of the hierarchical model are given in Section 7.7.1.3.

Simulation results presented in Section 7.7.1.6 demonstrate that under varying assumptions, this decision rule limits Type I error to approximately [REDACTED]

7.7.1.3. Bayesian Hierarchical Model

PFS will be modeled using an exponential likelihood model:

$$\lambda_T = \lambda \exp(\theta_T)$$

[REDACTED]

[REDACTED]

where λ_T is the hazard rate for the experimental arm, λ is the hazard rate for the control arm, and θ_T is the log hazard ratio between the hazard rates. [REDACTED]

[REDACTED]

[REDACTED]

7.7.1.4. Prespecified Historical Controls

Patient-level data was recovered from the Kaplan-Meier curves of the studies listed in [Table JP04.7.2](#). Among the  recovered datapoints, the observed hazard rate for PFS was . The estimated median PFS from the pooled data is was  months. These data will be incorporated using the hierarchical model described in Section [7.7.1.3](#) to inform the primary analysis of PFS.

Table JP04.7.2. Historical Controls for Ewing's Sarcoma Study

7.7.1.5. Additional Analyses of PFS

In addition to the primary analysis of PFS using the Bayesian hierarchical analysis described above, traditional (frequentist) assessments will be performed to provide additional context. The Kaplan-Meier (KM) method (Kaplan and Meier 1958) will be used to estimate the rPFS curves as well as rPFS rates at 3, 6, 9, and 12 months for each treatment group. The corresponding HR between treatment groups will be estimated using a stratified Cox regression model (Cox 1972), stratified by the randomization strata. An additional unstratified Cox regression model will be employed to explore the effects of the stratification variables on treatment response.

7.7.1.6. Simulation Results

Traditional operating characteristics were evaluated under varying assumptions of the true effect size and hazard rate. A total of 5000 trials were simulated for each scenario, and both the Bayesian analysis and traditional frequentist analysis are summarized in [Table JP04.7.3](#).

Table JP04.7.3. Simulation Results

7.7.1.7. Secondary Endpoint: PFS by Investigator Assessment

PFS by investigator assessment is a secondary endpoint in this study, and will be evaluated to determine futility planned futility analysis. At the futility analysis, the analyses of Section 7.7.1.5 will be performed. At the time of the primary analysis, all analyses specified for PFS by BIRC will be repeated for PFS by investigator assessment.

7.7.1.8. Sensitivity Analyses for Primary Progression-Free Survival Endpoint

Sensitivity analyses within the Bayesian framework will be conducted (1) including the stratification factors as covariates, (2) using alternative weakly informative priors for the control hazard rate, and (3) removing borrowing of historical control data.

If additional patient-level data suitable for inclusion with the historical control data in Table JP04.6.2 becomes available prior to the primary analysis, either the SAP will be updated with details, or sensitivity analyses incorporating the additional historical data may be performed if appropriate.

7.7.2. Secondary Efficacy Analyses

Overall survival (OS) is defined as the time from randomization until death from any cause. If the patient is alive or lost to follow-up at the time of data analysis, OS data will be censored on the last date the patient is known to be alive. The following analyses will be conducted for OS:

- Kaplan-Meier curves (Kaplan and Meier 1958) will be generated; medians, quartiles, and appropriate point probabilities will be calculated. Interval estimates will be calculated. The OS rates at 1, 2, and 3 years for each treatment group will be estimated and compared using a normal approximation for the difference between the rates
- The Cox regression stratified by the randomization factors will be used to estimate the HR between the 2 treatment groups.

Objective response rate (ORR) is defined as the number of participants who achieve a best overall response of CR or PR divided by the total number of participants randomized to the corresponding treatment arm (ITT population). The ORR, with CCI CI, will be summarized for each treatment arm and compared between treatment arms using the Cochran-Mantel-Haenszel test adjusting for the randomization strata.

Duration of response (DoR) is defined as the time from the date that measurement criteria for CR or PR (whichever is first recorded) are first met until the first date that disease is recurrent or documented disease progression is observed, per RECIST 1.1 criteria, or the date of death from any cause in the absence of documented disease progression or recurrence. DoR will be calculated only for patients with confirmed PR or CR. DoR will be summarized for each treatment arm using descriptive statistics.

Disease control rate (DCR) is defined as the number of participants who achieve a best overall response of CR, PR, or SD, divided by the total number of participants randomized to the corresponding treatment arm (ITT population). DCR will be summarized for each treatment arm using descriptive statistics.

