3.10.3.1.3. Objective Response Rate

Objective response rate is defined as the number of participants who achieve a best overall response of CR or PR divided by the total number of participants randomized to the corresponding treatment arm (ITT population). The ORR, with CCI CI, will be summarized for each treatment arm and compared between treatment arms using the Cochran-Mantel-Haenszel test adjusting for the randomization strata.

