3.10.3.1.4. Duration of Response

Duration of response is defined as the time from the date that measurement criteria for CR or PR (whichever is first recorded) are first met until the first date that disease is recurrent or documented disease progression is observed, per RECIST 1.1 criteria, or the date of death from any cause in the absence of documented disease progression or recurrence. Details can be found in the SAP.

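### DoR is restricted to confirmed responders while ORR states no confirmation condition, and DoR has neither a censoring rule nor a time-to-event estimator

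*SAP*

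**What the plan says.** **ORR.** SAP 7.7.2 counts the "number of participants who achieve a best overall response of CR or PR divided by the total number of participants randomized" to the arm. Protocol 3.10.3.1.3 uses the same definition: "Objective response rate is defined as the number of participants who achieve a best overall response of CR or PR". Neither text says whether best overall response needs confirmation, and neither gives a rule for deriving it. ORR is compared between arms with a stratified Cochran-Mantel-Haenszel test.

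**DoR.** Protocol 3.10.3.1.4 starts the clock at the first qualifying assessment, with no confirmation condition, and leaves details to the SAP: "Duration of response is defined as the time from the date that measurement criteria for CR or PR (whichever is first recorded) are first met". SAP 7.7.2 repeats that definition and then adds both a restriction and the method: "DoR will be calculated only for patients with confirmed PR or CR. DoR will be summarized for each treatment arm using descriptive statistics". The same descriptive wording is used for DCR, which is a simple proportion.

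**PFS and OS, for contrast.** PFS has the censoring scheme of Table JP04.7.1 and Kaplan-Meier estimation (SAP 7.7.1.5). OS has Kaplan-Meier and its own rule: "OS data will be censored on the last date the patient is known to be alive". PFS is also split explicitly into a BIRC endpoint and an investigator endpoint. No assessor is named for ORR, DoR or DCR.

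**The concern.** There are three gaps, all in sentences that are complete and not redacted.

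- **Responder set.** The confirmation condition is attached to DoR but not to ORR. As written, an analyst could count a patient in ORR and leave the same patient out of DoR.
- **Estimator.** DoR is a time-to-event quantity. The primary analysis is triggered by an event count (Protocol 3.10.3.1.1), so some responders may still be in response at the data cut. Nothing says how their durations enter the summary.
- **Assessor.** The trial is open-label, and Protocol 3.5.4 relies partly on blinded review for its integrity. Whether the tested ORR comparison uses BIRC or investigator reads is left open.

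At stake is whether the reported ORR and DoR can be read together, and whether the DoR figure means what readers will take it to mean. With about 15 control participants, the status of one or two responders is visible in the results.

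**Working it through.** The documents give no planning figure for ORR or DoR, so there is nothing to reproduce. What follows is illustration under stated assumptions.

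**Inputs from the documents**
- Cycles are 21 days, with scans at Cycles 3 and 5 and then every 3 cycles from Cycle 8 (Protocol 3.2). The gaps are 2 × 21 = 42 days and 3 × 21 = 63 days, or 6 and 9 weeks (1.38 and 2.07 months).
- At least 45 participants are randomized 2:1, giving about 30 in Arm A and 15 in Arm B.
- Background figures, not design assumptions: ORR 29% with mean DoR 30 weeks (Protocol 3.3.2.5), and ORR up to 63% (Protocol 3.3.1).

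**Assumptions**
- DoR is exponential with median 6 months, so the mean is m = 6/ln 2 = 8.66 months.
- Confirmation means still being in response and under follow-up at the next scan, g months after the first response.
- Censoring time from first response is uniform over 0–18 months (heavy) or 12–24 months (light).

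**Step 1: effect of the confirmation condition alone.** The share of responders lost is 1 − exp(−g/m), which is 14.7% at 6 weeks and 21.3% at 9 weeks. The true median among confirmed responders is g + 6, or 7.4 and 8.1 months, against 6.0 for all responders.

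**Step 2: effect of ignoring censoring among confirmed responders.** Under 0–18 months, the plain median t of observed times solves exp(−(t − g)/m) × (18 − t)/(18 − g) = 0.5.
- g = 1.38: at t = 5.15, 0.647 × 0.773 = 0.50.
- g = 2.07: at t = 5.78, 0.651 × 0.767 = 0.50.

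Under 12–24 months no one is censored before 12 months. The true medians lie below 12, so the plain median equals the true one. The completed-only medians below come from simulation.

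| Gap | True median, confirmed | Censoring | Plain median, all observed times | Plain median, completed only | Kaplan-Meier |
|---|---|---|---|---|---|
| 6 weeks | 7.4 | 0–18 | 5.2 | 4.5 | 7.4 |
| 9 weeks | 8.1 | 0–18 | 5.8 | 5.1 | 8.1 |
| 6 weeks | 7.4 | 12–24 | 7.4 | 6.1 | 7.4 |
| 9 weeks | 8.1 | 12–24 | 8.1 | 6.7 | 8.1 |

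(Months.)

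**Step 3: net effect against all responders.** Against the 6.0-month median for all responders, the plain median of all observed times is a little low under heavy censoring (5.2–5.8) and high under light censoring (7.4–8.1). The two mechanisms oppose each other, and the sign of the sum depends on follow-up.

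**Step 4: the protocol's 30-week mean instead.** The median for all responders is 30 × ln 2 = 20.8 weeks. The share lost is 1 − exp(−6/30) = 18% to 1 − exp(−9/30) = 26%.
- At ORR 29% this is 0.8–1.1 of 4.35 control responders (15 × 0.29) and 1.6–2.3 of 8.7 in Arm A (30 × 0.29).
- At ORR 63% it is 1.7–2.4 of 9.45 and 3.4–4.9 of 18.9.
- With a 6-week gap and censoring spread evenly up to 52 weeks (51% censored), the plain median among confirmed responders is 17.9 weeks against a true 26.8.

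**The case against.** **A reader might infer that ORR counts unconfirmed responders.** The documents do not say so. They are silent on whether best overall response is confirmed. Read together with the DoR sentence in the same section, it could be meant as confirmed, and then the two sets coincide. What stands is that the text does not settle it.

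**A reader might infer that DoR will be biased.** That is also not established. Nothing states that ongoing responses will be dropped or treated as complete. Descriptive statistics need not exclude a Kaplan-Meier median; SAP 7.10 uses the phrase for subgroup summaries that include PFS. Scans continue after treatment stops until progression (Table JP04.3), so heavy early censoring is not a given. The 12–24 month rows show that the plain median can be unaffected, although the completed-only median still falls short.

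**A reader might assume that BIRC response data will exist anyway.** Protocol 3.9.1 ties blinded review to the primary objective. It does not say that the review will deliver best response, confirmation and response dates.

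**The size is a proxy.** Treating unconfirmed as progressed or dead by the next scan is a simplification, because a response can go unconfirmed for other reasons.

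**The consequences are limited.** These endpoints are secondary and carry no multiplicity control, and DoR is not tested between arms. That bears on priority. It does not supply the missing rules.

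**Conclusion.** The point holds as a gap in specification. ORR and DoR may rest on different responders, and DoR lacks a censoring rule and a named time-to-event method. Understatement of DoR is conditional on ongoing responses being dropped or counted as complete. Under the exponential 6-month assumption the shortfall among confirmed responders is about 2.2–2.3 months with heavy censoring (7.4 − 5.2; 8.1 − 5.8). With light censoring it is nil for all observed times and about 1.3–1.4 months for completed responses only (7.4 − 6.1; 8.1 − 6.7). Relative to all responders, no net direction can be claimed. The change is worth making because it is cheap and ORR is formally compared between arms. The primary BIRC analysis of PFS and the futility rule are not affected.

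**What to change.** In SAP 7.7.2:

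1. State once whether a CR or PR must be confirmed, and use that responder definition for both ORR and DoR.
2. Estimate DoR in each arm by Kaplan-Meier, reporting the median with its confidence interval. Censor responders without an event by the rules of Table JP04.7.1. Kaplan-Meier deals with the censoring only; item 1 is what aligns the responders.
3. Name the assessor for ORR, DoR and DCR. Use BIRC reads if the central review provides response categories and dates, with investigator reads as supportive.

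Items 1 and 2 cost only SAP wording. Item 3 may also need a check of, or an addition to, what the central review delivers. If confirmation is required, ORR may be slightly lower.

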7.8. Bioanalytical and Pharmacokinetic/Pharmacodynamic Methods

Planned PK and PK/PD analyses are specified in a separate standalone PK/PD analysis plan.

7.9. Safety Analyses

Safety analyses will be based on the safety population, unless otherwise stated, and summarized by treatment arm corresponding to the actual regimen received at first dose.

Safety analyses will be completed as specified below, unless COVID-19 impact creates a situation requiring a change to an existing analysis or a need for additional analyses as outlined by Nilsson et al. (2020).

7.9.1. Extent of Exposure

Drug exposure, dose intensity, and drug adjustments (dose omissions and reductions) will be summarized for abemaciclib, for temozolomide, and for irinotecan. Drug exposure will include summaries of cycles received per patient, duration on therapy, and cumulative dose. Dose intensity will be calculated as the actual cumulative amount of drug taken divided by the duration of treatment. Relative dose intensity will be calculated as

$$\frac{\text{the amount of actual drug taken}}{(\text{the amount of drug prescribed})} \times 100\%$$

(expressed as a percentage). The summary of dose adjustments and omissions will include the reason for adjustment or omission.

Extent of exposure for abemaciclib will be measured by pill counts for tablets and capsules, and by weights for oral granules. Dose intensity will be expressed in mg/day. The assigned cumulative dose while on study is 2 doses per day \times planned amount of drug dose (dependent on dose level and patient BSA at the beginning of each cycle) \times number of days on treatment.

7.9.2. Adverse Events

The MedDRA Version 21.0 (or higher) will be used to map reported AEs to MedDRA terms. The MedDRA LLT will be used in the treatment-emergent computation. PTs identified as clinically identical or synonymous may be grouped together under a single consolidated PT. For

example, ‘Neutropenia’ and ‘Neutrophil count decreased’ may be aggregated and reported as ‘Neutropenia.’ The NCI CTCAE version 5.0 will serve as the reference document for grading the severity of all AEs and other symptoms.

Pre-existing conditions are defined as AEs that begin prior to the first dose of study treatment.

A TEAE is defined as any AE that begins between the day of first dose and 30 days after treatment discontinuation (or up to any time if serious and related to study treatment), or any preexisting condition that increases in CTCAE grade between the day of first dose and 30 days after treatment discontinuation (or up to any time if serious and related to study treatment). Comparisons of preexisting conditions to on-treatment events at the LLT level will be used in the treatment-emergent computation.

A SAE is any AE during this study that results in one of the following outcomes: death, initial or prolonged inpatient hospitalization, a life-threatening experience (that is, immediate risk of dying), persistent or significant disability/incapacity, congenital anomaly/birth defect, or considered significant by the investigator for any other reason. Additionally, important medical events that may not result in death, be life-threatening, or require hospitalization may be considered SAEs when, based on appropriate medical judgment, they may jeopardize the patient and may require medical or surgical intervention to prevent 1 of the outcomes listed in this definition.

Treatment-emergent adverse events will be summarized by SOC and by decreasing frequency of PT within SOC.

Safety analyses will include summaries of the following:

- AEs, including severity and possible relationship to study drug
- SAEs, including possible relationship to study drug
- AEs leading to dose adjustments
- discontinuations from study treatment due to AEs or death
- treatment-emergent abnormal changes in laboratory values
- treatment-emergent abnormal changes in vital signs.

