3.2. Schedule of Activities

This section includes the following SoA:

- Screening, Treatment, and Post-Discontinuation Follow-Up SoA for all participants
- Continued-Access SoA for participants on abemaciclib (See Section 7.8.1 of the CAMPFIRE Master Protocol for additional details)

Overview

The windows for the SoA and administration of first dose are based on calendar days.

At any time in the study, laboratory and pregnancy tests may be collected at a local clinic in accordance with local laws and regulations if deemed appropriate by the investigator. All results should be reviewed and recorded in the eCRF. A virtual visit with the study investigator is not required for a local lab draw or pregnancy test.

Screening and Baseline

The screening period allows up to 28 days for confirmation of eligibility and completion of baseline assessments.

Treatment Period

Cycles are 21 days. During the on-study treatment period, participants will return to clinic on Days 1-5 for IV infusions. Additional evaluations on Day 8 and Day 15 of each cycle will be conducted on-site, remotely (that is, by telephone, IT-assisted virtual visit, mobile healthcare, or a combination thereof) or a combination of remote and on-site at the direction of the sponsor, according to local laws and regulations.

Treatment will continue until disease progression, unacceptable treatment-related toxicity, or participant or physician decision to discontinue.

Tumor Response

Tumor response per RECIST 1.1 should be assessed approximately every 2 cycles (at Cycles 3 and 5) and then every 3 cycles (beginning Cycle 8) until the participant has objective disease progression, death, or study completion.

Short- and Long-Term Follow-Up

Participants discontinuing study intervention will return for a short-term follow-up visit (Visit 801). The short-term follow-up visit will take place 30 days (± 14 days) after the decision is made to discontinue all study treatment.

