3.7.8.2. Discontinuation of One Study Treatment

Participants may discontinue irinotecan and/or temozolomide (due to chemotherapy-associated toxicities) while continuing abemaciclib upon discussion with the Lilly CRP/CRS. If abemaciclib must be discontinued, participants may continue to receive irinotecan and/or temozolomide. For all study drugs, if dose reductions are required beyond the lowest dose, the drug should be discontinued. Continuation on chemotherapy beyond Cycle 12 will be up to the investigator's discretion and the individual participant's situation. Prior to continuing the participant on chemotherapy beyond Cycle 12, the investigator should discuss with the Lilly CRP/CRS. Abemaciclib may continue beyond Cycle 12 until discontinuation criteria is met.

Dose Modification for Neutropenia						
Note: For hematologic toxicities, dose holds, and reductions - apply simultaneously to all drugs as indicated						
	Abemaciclib		Irinotecan		Temozolomide	
Severity and Duration	Dose Hold	Dose Reduction	Dose Hold	Dose Reduction	Dose Hold	Dose Reduction
Grade 3	Recommend G-CSF in subsequent cycle					
Grade 4 Initial incident	Hold until ANC CCI	Consider 1 dose level reduction. If already taking G-CSF, reduce 1 dose level.	Hold until ANC CCI	Reduce 1 dose level	Hold until ANC CCI	No reduction Recommend G-CSF in subsequent cycle
Grade 4 >7 days duration or >14-day cycle delay		Reduce 1 dose level Recommend G-CSF in subsequent cycle		Recommend G-CSF in subsequent cycle		Reduce 1 dose level Recommend G-CSF in subsequent cycle
Grade 4 Recurrent ^a						Reduce 1 dose level Recommend G-CSF in subsequent cycle
Dose Modification for Febrile Neutropenia						
Note: For hematologic toxicities, dose holds, and reductions - apply simultaneously to all drugs as indicated						
Grade 3 Initial incident	Hold until resolution	Consider 1 dose level reduction Recommend G-CSF in subsequent cycle	Hold until resolution	Consider 1 dose level reduction Recommend G-CSF in subsequent cycle	No change	
Grade 3 Recurrent ^a				Reduce 1 dose level Recommend G-CSF in subsequent cycle		
Grade 4				Reduce 1 dose level Recommend G-CSF in subsequent cycle		Reduce 1 dose level if not previously on G-CSF Reduce 2 dose levels if G-CSF was used Recommend G-CSF in subsequent cycle

Abbreviations: ANC = absolute neutrophil count; G-CSF = granulocyte-colony stimulating factor.

Grade 3: ANC < 1000/mm³; **Grade 4:** ANC < 500/mm³.

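### TEAEs are summarised by arm over a window that lengthens with time on treatment, with no summary over a common period

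*SAP*

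**What the plan says.** SAP 7.9 presents safety data "summarized by treatment arm corresponding to the actual regimen received at first dose". SAP 7.9.2 then says: "Treatment-emergent adverse events will be summarized by SOC and by decreasing frequency of PT within SOC". A TEAE is "any AE that begins between the day of first dose and 30 days after treatment discontinuation", extended without limit for events that are serious and related, and it also covers worsening pre-existing conditions. The registry tables in SAP 7.14 use the number of participants at risk as denominator, not time at risk. SAP 7.9.1 summarises cycles received, duration on therapy and cumulative dose, but does not link them to AE incidence. Nothing in SAP 7.9 provides a time-adjusted rate, a time to first event or incidence over a common period.

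Three rules determine how long the window stays open. Treatment runs to progression, unacceptable toxicity or a decision to stop (Protocol 3.1 and 3.2). Protocol 3.7.8.2 lets a participant drop irinotecan and/or temozolomide for toxicity "while continuing abemaciclib upon discussion with the Lilly CRP/CRS". The same section treats the drugs differently after Cycle 12. Chemotherapy, which is all that Arm B receives, is left to the investigator's discretion: "Prior to continuing the participant on chemotherapy beyond Cycle 12, the investigator should discuss with the Lilly CRP/CRS". For the Arm A drug, "Abemaciclib may continue beyond Cycle 12 until discontinuation criteria is met".

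**The concern.** The length of the TEAE window depends on how long a participant is treated, and that can differ by arm in a predictable direction. A PFS benefit, which is what the trial hopes to show, lengthens treatment in Arm A. Abemaciclib continuing alone after chemotherapy keeps an Arm A window open at a point where an Arm B window would have closed. For toxicities that accrue with time, the side-by-side percentages then mix the rate of harm with time at risk, and the mixing grows with efficacy.

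Safety is a secondary objective, and readers of an open-label add-on trial will set the two columns against each other whether or not a test is run. The protocol itself treats some risks as time-dependent: Section 3.7.5 links Pneumocystis pneumonia to longer regimens. Infections, VTE, hepatic events and ILD are events of special interest (Section 3.9.2.1), and the documents do not describe them as confined to the early cycles.

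**Working it through.** The plan states no AE rate, expected exposure or unredacted design figure to reproduce, so this is a sensitivity calculation.

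**From the documents.** "Cycles are 21 days", so 12 cycles = 12 × 21 = 252 days = 8.28 months, and 4 cycles = 84 days = 2.76 months. The TEAE tail is 30 days, taken as 1 month. At least 45 participants at 2:1 gives about 30 versus 15.

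**Assumed.** Exponential time on treatment with an Arm B median of 5 months; hazard ratio 0.7 for stopping treatment; a 24-month limit on treatment; a constant event rate λ = 0.06 per month, equal in both arms. Then μ_B = ln 2 / 5 = 0.1386 and μ_A = 0.7 × 0.1386 = 0.0970.

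**Formula.** With treatment limited to c months, crude incidence = 1 − e^(−λ) × [ μ/(μ+λ) × (1 − e^(−(μ+λ)c)) + e^(−(μ+λ)c) ]. Mean time at risk = (1 − e^(−μc))/μ + 1.

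- Arm A, c = 24: μ+λ = 0.1570 and e^(−3.769) = 0.0231. Incidence = 1 − 0.9418 × (0.6179 × 0.9769 + 0.0231) = 41.0%. Mean time at risk is 10.3 months.
- Arm B, no stop at Cycle 12, c = 24: μ+λ = 0.1986 and e^(−4.767) = 0.0085. Incidence = 1 − 0.9418 × (0.6979 × 0.9915 + 0.0085) = 34.0%. Mean time at risk is 7.95 months.
- Arm B, everyone stopped at Cycle 12, c = 8.28: e^(−1.645) = 0.193. Incidence = 1 − 0.9418 × (0.6979 × 0.807 + 0.193) = 28.8%. Mean time at risk is 5.9 months.

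| Scenario (equal true rates) | Arm A | Arm B | Gap, points |
|---|---|---|---|
| HR 0.7, no Cycle 12 stop | 41.0% | 34.0% | about 7 |
| HR 0.7, all of Arm B stops at Cycle 12 | 41.0% | 28.8% | about 12 |
| HR 1, all of Arm B stops at Cycle 12 | 34.0% | 28.8% | about 5 |
| HR 1, no Cycle 12 stop | 34.0% | 34.0% | 0 |

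**Wider range.** Arm B medians of 3 to 8 months, λ from 0.02 to 0.30, no 24-month limit. Without the Cycle 12 stop the gap is 3 to 8 points at HR 0.7 and 7 to 16 at HR 0.5. With the stop it is 4 to 19 and 8 to 27.

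**Early-onset toxicity.** Suppose the rate is 0.25 per month for 63 days and zero after that, in both arms, with the main treatment-duration inputs and the Cycle 12 stop. Crude incidence is 39.5% versus 39.2%. In a wider check (medians 3 and 5, HR 0.7 and 0.5, rates 0.05 to 0.30) the gap is about 1 point at most.

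**Sampling error.** For 41.0% versus 34.0%, SE = √(0.410 × 0.590/30 + 0.340 × 0.660/15) = 15.2 points. For 41.0% versus 28.8% it is 14.7.

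**Testing two remedies under equal toxicity.**

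| Remedy | Constant 0.06 per month | Early only (0.25 per month for 63 days) |
|---|---|---|
| Incidence within Cycles 1-4 (84 days), with Cycle 12 stop | 14.5% vs 14.2% | 39.5% vs 39.2% |
| First events per person-month, with Cycle 12 stop | 0.060 vs 0.060, ratio 1.00 | 0.061 vs 0.100, ratio about 0.6 |
| First events per person-month, no stop | ratio 1.00 | ratio about 0.8 |

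The common window is close to equal in both patterns. The person-time rate is right only when the rate is constant. With early toxicity it credits the longer-treated arm with event-free time after the risk has passed.

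**The case against.** A reader might infer that Arm B is capped at Cycle 12 and that the tables will therefore show a spurious 12-point excess. The documents do not support that. Protocol 3.7.8.2 leaves later chemotherapy to discretion after a sponsor discussion, so 12 points is a limiting case; without the stop, the same inputs give 7.

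Nor is every extra Arm A event an artefact. After chemotherapy stops, Arm A participants may be on abemaciclib and Arm B participants on nothing. Drug-caused events in that period are real harm from the Arm A regimen, and cumulative incidence over the assigned regimen is a legitimate quantity. The equal constant rate is a device for isolating the effect of time and has no support in the documents. Their clearest timing statement about a study toxicity points the other way: abemaciclib diarrhea is most frequent in early cycles (Protocol 3.7.4.6.3 and the diarrhea table in 3.7.8.3.2), where the gap almost vanishes.

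The plan summarises by arm and plans no AE test. The exposure summaries in SAP 7.9.1 let a reader see unequal durations. The standard error exceeds the gap in both main scenarios. Finally, Protocol 3.10.3.2 also refers to CAMPFIRE Master Protocol Section 10.3.1, which was not available; it may already contain a suitable summary.

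All of this stands, and it limits the size of the point and the choice of remedy. It does not remove the point. Sampling noise does not cancel a shift whose direction is known once Arm A is treated longer, and a separate exposure table does not tell the reader how much of an AE difference is due to duration.

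**Conclusion.** The concern holds in a conditional form. If Arm A is treated longer, through a PFS benefit or through abemaciclib outlasting chemotherapy, the percentages planned in SAP 7.9.2 will be higher in Arm A for toxicities that accrue over time, even at equal monthly rates. SAP 7.9 has no summary that separates the two. About 7 points is a reasonable illustration under the assumed median, hazard ratio and event rate, with a range from 0 to well above 12 depending on exposure that the documents do not give.

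A reader might also infer that exposure-adjusted rates should replace the crude figures in between-arm statements. They should not: for early-onset events they can make Arm A look safer than it is, by a ratio of about 0.6 to 0.8 in the example. This is a modest, inexpensive improvement to safety reporting and does not bear on the primary analysis.

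**What to change.** In SAP 7.9.2, for any TEAE, Grade 3 or higher TEAEs, SAEs and the events of special interest:

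- Add incidence by arm within a fixed early window common to both arms, for example Cycles 1-4. Defining it as 84 days from first dose (4 × 21) avoids a window that stretches with cycle delays. Refer to this table when describing differences between arms.
- Keep the crude tables as the record of the cumulative toxicity of each regimen and for registry reporting.
- If exposure-adjusted first-event rates are added, label them as context, with a note that they assume a constant rate and favour the longer-treated arm for early-onset events.
- If Master Protocol Section 10.3.1 already provides a common-window summary, a cross-reference is enough.

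Cost: a few lines in the SAP and one or two extra tables, using AE dates and exposure already collected. The drawback is that an early window says nothing about late toxicity, so the crude tables must stay beside it.
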